4.2.1.1 Handling missing data for the primary efficacy variable

Missing data for co-primary efficacy variables will be imputed using NRI as primary method. That is, subjects with missing data at Week 16 or who discontinue treatment prior to Week 16 will be counted as non-responders for the analysis.

In addition, sensitivity analyses using multiple imputation (Markov-Chain Monte Carlo method) (MI-MCMC)/monotone regression, last observation carried forward (LOCF) and observed case (OC) method will be performed which will assess the impact of different methods of handling missing data. These methods are described in Section 8.1.3.1 to Section 8.1.3.2.

4.2.1.2 Handling missing data for the secondary efficacy variables

For secondary binary efficacy variables, missing data will be imputed using NRI as primary method. MI-MCMC/monotone regression and OC methods will be performed as sensitivity analysis.

For secondary continuous efficacy variables, MI-MCMC/monotone regression is the primary method for imputing missing data. If the imputation model cannot converge, last observation carried forward (LOCF) will be used. OC method will be performed as sensitivity analysis.

4.2.1.3 Handling missing data for the other efficacy variables

For other binary efficacy variables, missing data will be imputed using NRI as primary method.

For other continuous efficacy variables, MI-MCMC/monotone regression method will be used to impute missing data as primary method. If the imputation model cannot converge, last observation carried forward (LOCF) will be used.

For other ordinal variables (EQ-5D-3L and Patient Global Assessment of PSO), OC method will be applied as the primary analysis method. No imputation is applied.

For those other efficacy variables that were included in the sequence testing procedure, OC method will also be applied as sensitivity analysis.

4.2.1.4 Handling missing data for subgroup analyses

For subgroup analyses specified in Section 4.8, NRI will be used for responder variables. Only descriptive statistics will be provided.

4.2.1.5 Missing Data Overview and Summary

In summary, the approaches listed below will be used in this study for handling missing data for efficacy variables as appropriate:

- Non-responder imputation (NRI): Subjects who have missing data at the time point of interest are treated as though they did not respond to the treatment.
- Multiple Imputation (MI) – Markov Chain Monte Carlo (MCMC) / Monotone Regression: Using multiple imputation methodology, intermittent missing data are imputed based on the MCMC method, and monotone missing data are imputed using monotone regression. Note: for all analyses and summaries using MI, subjects with no baseline value will be excluded.
- Last observation carried forward (LOCF): Post-Baseline missing data are imputed by carrying forward the last available observation (including Baseline).

- Observed case (OC): Missing data are not imputed. Only subjects with available data who have not discontinued study treatment at the given time point are considered.

The following table depicts which missing data handling approaches should be used based on variable priority (primary, secondary, other) and variable type (responder, continuous, ordinal).

Table 4–1: Missing data handling approach by variable priority and type

Variable Priority	Variable Type	NRI	MI (MCMC/ Monotone Regression)	MI (MCMC/ Reference-based)	LOCF	OC
Primary	Responder	P	S ^a	n/a	S	S
Secondary	Responder	P	S ^a			S
	Continuous		P		B	S
Other	Responder	P				S ^{b, c}
	Continuous ^e		P		B	
	Ordinal					P ^d

P=Primary method, S=Sensitivity method, B=Backup method, NRI=Non-responder imputation, MI=Multiple imputation, MCMC=Markov Chain Monte Carlo, LOCF=Last observation carried forward, OC=Observed Case
Note: Backup method is only applicable when the primary method is unable to converge due to challenges with the imputation model.

^a Imputation method is applied on continuous data, and responder variable is derived from the continuous variable based on complete data set.

^b Only applies to by-visit summaries of variables that are in the multiplicity-controlled testing procedure.

^c Includes IGA response, PASI75, PASI90 and PASI100.

^d Includes Patient Global Assessment of PSO, IGA score and EQ-5D-3L responses.

^e For PASE, OC is the primary analysis method.

4.2.1.6 Missing data algorithms

MI – MCMC / Monotone Regression

Investigators will be given discretion to discontinue study treatment for subjects not responding in order to provide them with alternative therapy to treat the condition. Therefore, in many cases, missing efficacy data due to study treatment discontinuation should be dependent on the observed efficacy scores, but independent of unobserved data. This would be consistent with a missing at random (MAR) pattern of missingness. To investigate the efficacy results under the assumption of data being MAR, a multiple imputation method will be applied as follows:

1. Create a data set, one for each treatment group (note that a separate imputation procedure must be invoked in SAS for each treatment group as the seed cannot be set for by groups beyond the first when using a by statement), of subjects with observed values and those needing estimation by multiple imputation. The intermittent missing PASI/IGA values in each data set (ie, missing values for a given subject that has available data before and after the missing time point) will be filled in using the MCMC method, with a total of 100 sets of imputations being performed. The seed used for these imputations will be 852 (note that all other multiple imputation procedures described in this SAP related to

MCMC / Monotone Regression analyses will use this same seed as well). For monotone missing data (ie, where all subject data is missing after a given time point), monotone regression then will be used to impute missing data. This will be based on the 100 sets of imputations already created using the MCMC method such that there will be 100 imputations in total. In both cases, biologic exposure, geographic region and PASI/IGA values at Baseline and at each post-Baseline visit (in chronological order, see notes below about visits to include for different analysis sets) will be included in the imputation model. Note that PASI scores at earlier visits will also be used as predictors for the model of PASI at later visits. The resulting data sets for each treatment arm will be combined into one complete data set based on each of the 100 imputations.

Note: The imputation model will only allow continuous variables. Therefore, prior biologic exposure and region will be re-coded as indicator variables. For prior biologic exposure, this will simply be 0 for biologic-naïve subjects and 1 for biologic-exposed subjects. For region, which has 4 levels, one indicator variable will be defined as 0 for regions other than North America and 1 for North America. Two more indicator variables will be defined similarly replacing North America with Central/Eastern Europe, and Western Europe respectively. An indicator variable for Asia/Australia is not needed as the fourth region will be adequately represented by the other region indicator variables all being 0. In the event that the number of randomized subjects is less than 10% in either of the Asia/Australia or Western Europe regions, then the two regions will be combined as a geographic region stratum for efficacy modeling, so that there are no modeling convergence issues across efficacy variables. In order to achieve model convergence, prior biologic exposure may be dropped from the model. If convergence is still not obtained, then region may also be dropped from the model.

2. For each complete imputed data set, the dichotomous responder variable (PASI90/IGA 0 or 1) based on the PASI/IGA scores will be computed. Each complete imputed data set will then be analyzed based on the stratified CMH test.

Note: For derivation of PASI90 response, the PASI value at Week 16 in the imputed data sets will be compared directly to the observed Baseline PASI value to determine whether or not a reduction of at least 90% was achieved. If values outside of the pre-defined range of values for PASI (0-72) are imputed, they will be cut off as appropriate after the multiple imputation procedure but before deriving the responder variable. For example, an imputed PASI value of -0.5 would be changed to 0 before deriving the PASI90 responder variable.

Note: Standard rounding rules will be applied to the imputed IGA values in order to derive the binary IGA 0/1 responder variable. In addition, if values outside of the pre-defined range of values for IGA (0-4) are imputed, they will be cut off as appropriate after the multiple imputation procedure but before deriving the responder variable. For example, if a subject has an IGA score imputed as 1.4 (and assuming a Baseline IGA score of 3), this imputed value would be rounded down to 1, and the minimum change

from Baseline of 2 would have been met. Therefore, this subject would be considered an IGA 0/1 responder.

Additional ranges of values for other variables are defined in [Table 4–2](#).

Table 4–2: Imputation allowable ranges by variable

Variable	Minimum value	Maximum value	Integer values only
PASI	0	72	No
IGA	0	4	Yes
PSD item	0	10	No
Scalp IGA	0	4	Yes
mNAPSI	0	130	No
BSA	0	100	Yes
IGAxBSA	0	400	Yes
DLQI	0	30	Yes
PGADA	0	100	Yes
SF-36	0	100	No
EQ-5D-3L VAS	0	100	Yes
WPAI dimension scores	0	100	No for variables “Percent work time missed due to problem” and “Percent overall work impairment due to problem”. Yes for variables “Percent impairment while working due to problem” and “Percent activity impairment due to problem” These two variables can only take values that are multiples of 10”
PHQ-9	0	27	Yes

- The Week 16 results from the specified statistical analysis (e.g. stratified CMH, logistic regression) of each of the 100 imputed data sets will be combined for overall inference using Rubin’s rules, which account for the uncertainty associated with the imputed values (Rubin, 1987). This will be done using SAS PROC MIANALYZE.

Note that this procedure indicates that the imputation model will be applied for each treatment group separately in PROC MI, which will be the default method. However, in the event there are computational challenges with the imputation model (eg, due to a standard deviation of 0 for responses of a given imputation), it is acceptable to modify the imputation model to include treatment as a variable in the model rather than running a separate model for each treatment group. It should be noted that doing so assumes that treatment does not interact with any of the other variables in the imputation model.

Some further details about imputation for different analysis sets are provided below:

- Randomized Set: When programming multiple imputation based on the RS, PROC MI will be used with a separate data set for each of the 3 randomized treatment groups (Bimekizumab 320mg Q4W, Bimekizumab 320mg Q8W, Adalimumab). For Bimekizumab 320mg Q4W and Bimekizumab 320mg Q8W, include all scheduled assessment visits from Baseline to Week 56. For the Adalimumab group, include only scheduled assessments from Baseline to Week 24. NOTE: The combined Bimekizumab 320mg group will not be run through PROC MI. The combined group will be obtained by using the imputed values of the individual Q4W and Q8W groups
- Bimekizumab Week 24 Set: When programming multiple imputation based on the BKZ Week 24 Set, PROC MI will be used with a separate data set for each of the 3 randomized treatment groups (Bimekizumab 320mg Q4W, Bimekizumab 320mg Q8W, Adalimumab) including all scheduled assessment visits from Baseline to Week 56. NOTE: The combined Bimekizumab 320mg group will not be run through PROC MI. These tables will only present the 3 treatment sequences (no BKZ Total needed).

Some key points to consider relative to the calculation of the odds ratios and corresponding confidence intervals are noted below:

If stratified CMH or logistic regression are used, the estimates of the odds ratios from the logistic regression model in step 3 follow a log-normal distribution, and a log transformation is needed to normalize these estimates since the procedures for combining results from multiple imputed datasets are based on the assumption that the statistics estimated from each imputed dataset are normally distributed. Therefore, the log of the odds ratio estimates from the logistic regression model are used when combining into a single inference (the use of PROC MIANALYZE in step 3). Appropriate transformations to the standard errors and p-values should also be made in order to get the correct confidence intervals. For the CMH test using the p-value for the general association the Wilson-Hilferty transformation should be used (Ratitch, 2013).

Missing data for continuous primary or secondary efficacy variables will be imputed using MI as appropriate. The MI procedure for continuous variables will be similar to that described above with the following differences:

1. The absolute value of the given variable will be imputed. Once imputation has been performed across the 100 iterations specified, any values outside of the range of the given variable will be truncated accordingly.
2. The change from Baseline values will be computed based on the complete data sets.
3. The analysis model will be based on ANCOVA (see above) as opposed to the CMH test.

For other continuous efficacy variables, MI will be used to impute missing data when possible. If the imputation model cannot converge, LOCF will be used. The MI procedure will also be similar to that described above with the following differences: 1) No dichotomization will be necessary; 2) instead of using the stratified CMH test or logistic regression, the imputed data sets will be combined and simple means and standard errors will be calculated using Rubin's rules (via SAS PROC MIANALYZE). For calculation of other descriptive statistics such as the median, min and max, Rubin's rules do not apply. Multiple imputation estimates will be computed by simply averaging the estimates from the multiple repetitions of the imputation algorithm. This is the same approach that will be used when summarizing continuous secondary efficacy variables by subgroup.

4.2.2 Handling missing data for safety variables

For analyses of AEs and concomitant medication usage, a complete date must be established in order to correctly identify the AE or medication as occurring during treatment or not. For purposes of imputing missing components of partially-reported start and stop dates for AEs and for medication use, the algorithms listed below will be followed. Start and stop dates of AEs or concomitant medication will be displayed as reported in the subject data listings (i.e., no imputed values will be displayed in data listings).

Partial AE and concomitant medication start dates will be imputed as follows:

Imputation of Partial Start Dates

- If only the month and year are specified and the month and year of first dose is not the same as the month and year of the start date, then use the 1st of the month
- If only the month and year are specified and the month and year of first dose is the same as the month and year of the start date, then use the date of first dose
- If only the year is specified, and the year of first dose is not the same as the year of the start date, then use the 1st of January of the year of the start date
- If only the year is specified, and the year of first dose is the same as the year of the start date, then use the date of first dose
- If the start date is completely unknown and the stop date is unknown or not prior to the date of first dose, then use the date of first dose.

Imputation of Partial Stop Dates

- If only the month and year are specified, then use the last day of the month
- If only the year is specified, then use December 31st of that year
- If the stop date is completely unknown, do not impute the stop date.

In the event of ambiguity or incomplete data which makes it impossible to determine whether a medication was concomitant or an adverse event was treatment emergent, the medication will be considered as concomitant or the adverse event will be considered treatment emergent.

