6.4 Prior and concomitant medications

Medication start and stop dates will be compared to the date of first dose of treatment to allow medications to be classified as either Prior or Concomitant.

Details of imputation methods for missing or partial dates are described in Section 4.2.2.

Prior medications include any medications that started prior to the start date of study medication.

Concomitant medications are medications taken at least one day in common with the study medication dosing period.

The number and percentage of subjects taking prior medications (excluding past psoriasis medications) will be summarized by treatment group, overall and by Anatomical Therapeutic Chemical classification (ATC) class, presenting Anatomical Main Group (ATC Level 1), Pharmacological Subgroup (ATC level 3), and preferred term. The number and percentage taking concomitant medications will be summarized similarly.

Past psoriasis medications will be captured separately and will also be summarized by treatment group. These medications are not subject to dictionary coding. In addition, subjects who failed past psoriasis biologic treatment will be summarized by reason of failure as captured on the Psoriasis Treatment History CRF module.

By-subject listings of all Prior and Concomitant medications, prior and concomitant medications glossary, and psoriasis treatment history will be provided.

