10.2.1 Data considerations

Treatment-emergent AEs (TEAEs) are defined as those AEs that have a start date on or following the first dose of study treatment through the final dose of study treatment + 140 days

(covering the 20-week SFU period). If it is not possible (due to partial dates) to determine whether or not an AE is treatment-emergent then it will be assumed to be a TEAE.

The rules for imputing partial start or stop dates are outlined in Section 4.2.1.2.

If the intensity of an adverse event is unknown, it is considered as severe. If the relationship to study drug is missing, it is considered as related.

AEs will be presented as “number of subjects (percentage of subjects) [number of events]”. In this style of output, “[number of events]” will include all cases of an AE including repeat occurrences in individual subjects, while “number of subjects” will count each subject only once.

Subject time at risk represents the time a subject is at risk for having an AE. The definitions for subject time at risk (in days) are outlined in Section 10.1. These definitions will be used for exposure-adjusted AE summaries.

Selected AE summaries will include the exposure adjusted incidence rate (EAIR) with associated 95% confidence interval and the exposure adjusted event rate (EAER).

The EAIR is defined as the number of subjects (n) with a specific AE adjusted for the exposure and will be scaled to 100 patient-years:

$$EAIR = 100 \times n / \sum_{i=1}^N (T_{Exp(i)})$$

Where $T_{Exp(i)}$ is the exposure time and N is the number of subjects at risk.

If a subject has multiple events, the time of exposure is calculated to the first occurrence of the AE being considered. If a subject has no events, the total time at risk is used.

Exact Poisson 95% confidence intervals for incidence rates are calculated using the relationship between the Poisson and the Chi-square distribution (Ulm, 1990; Fay and Feuer, 1997):

$$LCL = \chi^2_{2n, \alpha/2} / 2$$

$$UCL = \chi^2_{2(n+1), \alpha/2} / 2$$

where n is the number of subjects with a specific AE for the incidence rate of interest and is the basis for the number of the degrees of freedom for the chi-square quantile for the upper tail probability χ^2 .

The EAER will be the number of AEs including repeat occurrences in individual subjects divided by the total time at risk scaled to 100 patient-years and calculated using:

$$EAER = 100 \times N_{AE} / \sum_{i=1}^N (T_{Risk(i)})$$

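### Two of the SAP's partial start-date rules ignore the stop date, so an adverse event known to have ended before first dose can be counted as treatment-emergent

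*SAP*

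**What the plan says.** SAP 4.2.2 has five bullets for partial start dates. Two apply when the reported month or year differs from that of first dose, and give the 1st of the month or 1 January. The other three assign the first-dose date:

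- Month and year reported, and both matching first dose; this bullet ends "is the same as the month and year of the start date, then use the date of first dose".
- Year only reported, when "the year of first dose is the same as the year of the start date, then use the date of first dose".
- No start information: "If the start date is completely unknown and the stop date is unknown or not prior to the date of first dose".

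Only the last of these refers to the stop date. For partial stop dates, the SAP says: "If only the month and year are specified, then use the last day of the month". A year-only stop becomes 31 December, and a missing stop is left missing.

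A closing default in 4.2.2 covers unresolved records. It begins "In the event of ambiguity or incomplete data which makes it impossible to determine whether a medication was concomitant" and settles such records as concomitant or treatment-emergent. SAP 10.2.1 has a similar default for TEAEs.

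The classifications that use these dates are:

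- SAP 10.2.1: "Treatment-emergent AEs (TEAEs) are defined as those AEs that have a start date on or following the first dose of study treatment", up to 140 days after the final dose. The stop date plays no part.
- SAP 6.4: "Prior medications include any medications that started prior to the start date of study medication". A concomitant medication must share at least one day with the dosing period.

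Adverse events are recorded from signature of the consent form (protocol 12.1.1.1), and screening lasts 2 to 5 weeks (SAP 2.3.2.1). Events that begin and end before first dose are therefore in the database.

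**The concern.** The SAP treats a record with no start information more carefully than one with some. If the start is wholly unknown and the stop precedes first dose, no first-dose start is assigned. If the month or year happens to be known and matches first dose, the first-dose date is assigned even though the stop date already shows that the event was over. The derived data then hold a start later than the stop, and TEAE status, which depends on the start alone, comes out wrong.

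At stake are TEAEs and SAEs adjusted for exposure, which are secondary safety variables (protocol 4.2.2), and the split between prior and concomitant medication.

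**Working it through.** The plan gives no figure to reproduce. The check was to apply the five start rules and three stop rules of SAP 4.2.2 literally to test records, and then the definitions in SAP 10.2.1 and 6.4. The first-dose date of 20 June 2018 is an assumption chosen for illustration.

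| Case | Reported start | Reported stop | Imputed start | Stop used | Start after stop? | TEAE (if an event) | Prior / overlaps dosing (if a medication) |
|---|---|---|---|---|---|---|---|
| A | Jun 2018 | 12 Jun 2018 | 20 Jun 2018 | 12 Jun | yes, 20 − 12 = 8 days | yes | no / no |
| B | 2018 | 30 May 2018 | 20 Jun 2018 | 30 May | yes, 1 + 20 = 21 days | yes | no / no |
| C | 2018 | May 2018 | 20 Jun 2018 | 31 May (imputed) | yes, 20 days | yes | no / no |
| D | Jun 2018 | Jun 2018 | 20 Jun 2018 | 30 Jun (imputed) | no | yes | no / yes |
| E | unknown | 12 Jun 2018 | none | 12 Jun | – | not assigned | not assigned |
| F | May 2018 | 12 Jun 2018 | 1 May 2018 | 12 Jun | no | no | yes / no |
| G | 2017 | 12 Jun 2018 | 1 Jan 2017 | 12 Jun | no | no | yes / no |

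Cases A to C are wrong: in each, the stop date (reported, or imputed by the SAP's own rule) lies before first dose. Case D is truly undetermined, and treating it as emergent is what the SAP intends. Cases E to G are handled properly. The defect is therefore limited to records with (i) a partial start matching first dose on month and year, or on year when only the year is given, and (ii) a stop, reported or imputed, before first dose.

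**Do the defaults rescue A to C?** No. They apply where status cannot be determined, and a stop before first dose determines it.

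**Which tables are reached?** The false onset is always the first-dose date. Against the five presentations of the main TEAE tables in SAP 10.2.2:

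- Initial period, Safety Set: affected.
- Through Week 24, Safety Set: affected.
- Initial and maintenance period, BKZ Set: affected for subjects randomized to bimekizumab. For the adalimumab arm this set covers bimekizumab treatment only (SAP 10.1.3), so an onset on the first adalimumab day does not belong in it.
- Maintenance period, Maintenance Set: not affected.
- Week 24 to 56, adalimumab switchers: not affected.

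**Effect per record.** If the subject has no other event in the same table row, one false TEAE adds 1/150 = 0.7 percentage points to the incidence in a 150-subject arm, or 1/300 = 0.3 points in the pooled bimekizumab group. In the exposure-adjusted incidence rate it adds one to the numerator. It also cuts that subject's time for the event to almost nothing, because time runs to first occurrence (SAP 10.2.1).

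**With the stop-date condition added.** Case A gives 1 June 2018, and B and C give 1 January 2018: not TEAE, prior, not concomitant. Case D is unchanged.

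**The case against.** The strongest reply is that the SAP's intent is clear from its other sections. SAP 3.9 recognises non-treatment-emergent events that began and ended before first dose, and the assume-emergent defaults are reserved for undeterminable records. A sensible programmer might add the missing check unprompted. The error also over-counts TEAEs, as the defaults do; adverse-event summaries are descriptive and lie outside the testing sequence (SAP 4.5); and listings show dates as reported, so an affected record can be found. All of this limits the harm, but it does not cure the text. The two bullets give an explicit instruction, and it conflicts with that intent.

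Three stronger readings are tempting, and the documents do not support them.

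- A reader might infer that every TEAE table is wrong. An onset fixed at first dose cannot enter the maintenance-only or post-switch tables.
- A reader might infer that affected medications vanish from both medication tables. That follows from applying the two SAP 6.4 definitions to the imputed start. The same section also says that start and stop dates are compared with first dose so that each medication falls into one class or the other. A program that checks only whether the start is on or after first dose would label the record concomitant; one that checks overlap would leave it in neither class. What does stand is that it is no longer prior.
- A reader might expect many such medications because psoriasis drugs are washed out before Baseline. Past psoriasis medications are excluded from the prior-medication table and captured separately (SAP 6.4).

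**Conclusion.** The point holds as a defect of the rule as written. Two of the three bullets that assign the first-dose date lack the stop-date condition that the third carries. Any record that meets conditions (i) and (ii) in the working is misdated if the bullets are followed literally.

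The documents give no count of partial dates, so the total effect cannot be computed. It is probably small, because an affected event needs an onset after consent, a matching partial start and a stop before dosing. These events precede dosing in a randomized, blinded trial, so no imbalance between arms is expected. Efficacy is untouched. The conclusion rests on the program following 4.2.2 literally, which the documents neither confirm nor rule out. The correction is worth making because the rule can produce impossible dates and costs almost nothing to mend, not because it threatens the trial's safety conclusions.

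**What to change.** In SAP 4.2.2, add to the month-and-year and year-only bullets that the first-dose date is assigned only when the stop date, reported or imputed, is missing or falls on or after first dose. Otherwise impute the 1st of the reported month, or 1 January of the reported year. For adverse events, go no earlier than the consent date, since events are collected only from then and 1 January could precede it. State as a general limit that no imputed start may be later than the reported or imputed stop; the limit has to cover imputed stops because case C depends on one.

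The cost is about one sentence in the SAP and one condition in the derivation program. A listing of records whose derived start is later than the stop would show how many were affected.
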